## 6.5. Efficacy Analysis

Analyses of the exploratory efficacy endpoints (incidence rates in COVID-19, SARS-CoV-2 infection, and asymptomatic infection) will be performed using the PP Set for Efficacy and mITT1 Set for long-term and Part 1C-1, and using the FAS for Part 1C-2, Part 2 and Part 3. The PP Set for Efficacy used in blinded phase for mRNA-1273 arm and the mITT1 Set for the long-term analysis will be used for the efficacy analysis in the long term including both the blinded and open label phases; the mITT1 Set for the booster-dose Part 1C-1 will be used for the efficacy analysis in the Part 1C-1 booster dose phase; the FAS will be used for the efficacy analysis in Part 1C-2, Part 2 and Part 3, unless otherwise specified. Subjects will be included in the vaccination group as defined in Section 6.1.

**Baseline SARS-CoV-2 status and Pre-booster SARS-CoV-2 status** is described in [Section 6.1](#). Baseline SARS-CoV-2 status in Part 2 and Part 3, Pre-booster SARS-CoV-2 status in Part 1C-1 and Part 1C-2, the serology test results based on *Roche Elecsys* assay and the RT-PCR test results will be summarized by treatment group.

For mRNA-1273 arm, PP Set for Efficacy and mITT1 set is same as those used in blinded phase. For Placebo-mRNA-1273 cross-over arm, participants with positive or missing SARS-CoV-2 status before the first dose of mRNA-1273 will be excluded from the mITT1 Set for long-term efficacy analysis.

Participants with pre-booster positive or missing SARS-CoV-2 status will be excluded from the mITT1 Set for Part 1C-1 booster dose efficacy analysis.

The serology test results based on Roche Elecsys assay and the RT-PCR test results will be summarized by visit.

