### **3.3.4. Exploratory Endpoints**

The exploratory endpoints are the following:

- The GM values of SARS-CoV-2 S2P specific bAb on BD-Day 1, BD-Day 29 (1 month after BD), BD-Day 181 (6 months after BD), and BD-Day 361 (1 year after BD)
- The GM values of SARS-CoV-2-specific nAb on BD-Day 1, BD-Day 29 (1 month after BD), BD-Day 181 (6 months after BD), and BD Day 361 (1 year after BD)
- The incidence of SARS-CoV-2 infection (symptomatic or asymptomatic infection) counted starting 14 days after BD of mRNA-1273
- To evaluate the incidence of asymptomatic SARS-CoV-2 infection after vaccination with mRNA-1273 measured by RT-PCR and/or bAb levels against SARS-CoV-2 nucleocapsid protein (by Roche Elecsys) counted starting 14 days after BD in participants with negative SARS-CoV-2 at baseline or prebooster
- The incidence of the first occurrence of symptomatic COVID-19 starting 14 days after BD of mRNA-1273

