### **3.4.3. Exploratory Endpoints**

The exploratory endpoints are the following:

- The GM values of SARS-CoV-2 S2P specific bAb on Day 1, Day 57 (1 month after Dose 2), Day 209 (6 months from Dose 2), Day 394 (1 year from Dose 2)
- The GM values of SARS-CoV-2-specific nAb on Day 1, Day 57 (1 month after Dose 2), Day 209 (6 months from Dose 2), Day 394 (1 year from Dose 2)
- The incidence of SARS-CoV-2 infection (symptomatic or asymptomatic infection) counted starting 14 days after Dose 2 of mRNA-1273

- To evaluate the incidence of asymptomatic SARS-CoV-2 infection after vaccination with mRNA-1273 measured by RT-PCR and/or bAb levels against SARS-CoV-2 nucleocapsid protein (by Roche Elecsys) counted starting 14 days after Dose 2 in participants with negative SARS-CoV-2 at baseline
- The incidence of the first occurrence of symptomatic COVID-19 starting 14 days after Dose 2 of mRNA-1273

### 3.5. Part 3

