##### The Full Analysis Set (FAS) (Part 2, Part 3)

The FAS for Part 2 and Part 3 consists of all participants who received at least one dose of IP in each part. Participants will be analyzed according to the treatment group assigned.

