### **6.5.1. Endpoint Definition/Derivation**

#### **6.5.1.1. Derivation of SARS-CoV-2 Infection**

This is an exploratory efficacy endpoint, which is a combination of COVID-19 and asymptomatic SARS-CoV-2 infection for participants with negative SARS-CoV-2 status at baseline (for mRNA-1273 group in long-term analysis), pre-dose 1 of mRNA-1273 (for Placebo-mRNA-1273 group in long-term analysis), or pre-booster dose (for Part 1C-1 booster dose analysis), the incidence of SARS-CoV-2 infection counted starting 14 days after the second dose of mRNA-1273 in long-term (including Part 1B), and cases counted starting 14 days after the booster dose of mRNA-1273 in Part 1C-1. SARS-CoV-2 infection will be defined in participants with negative SARS-CoV-2 at baseline of each part (pre-dose 1 of mRNA-1273 or pre-booster dose):

- bAb level against SARS-CoV-2 nucleocapsid protein negative (as measured by *Roche Elecsys*) at baseline of each part that becomes positive (as measured by *Roche Elecsys*) post-baseline, OR
- Positive RT-PCR post-baseline.

Derivation of this secondary efficacy endpoint is summarized in Table 1 below.

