#### **6.5.1.2. Derivation of Asymptomatic SARS-CoV-2 Infection**

This is an exploratory efficacy endpoint: the incidence of asymptomatic SARS-CoV-2 infection measured by RT-PCR and/or serology tests obtained at post-baseline visits counted starting 14 days after the second injection of mRNA-1273 in long-term (including Part 1B), and cases counted starting 14 days after the booster dose of mRNA-1273 in Part 1C-1, in participants with negative SARS-CoV-2 status at baseline of each part.

Asymptomatic SARS-CoV-2 infection is identified by absence of symptoms and infections as detected by RT-PCR or serology tests. Specifically:

- Absent of COVID-19 symptoms
- AND at least one from below:
  - bAb level against SARS-CoV-2 nucleocapsid protein negative (as measured by Roche Elecsys) at baseline of each part that becomes positive (as measured by Roche Elecsys) post-baseline, OR
  - Positive RT-PCR test post-baseline (at scheduled or unscheduled/illness visits)

The date of documented asymptomatic infection is the earlier date of positive serology test result based on bAb specific to SARS-CoV-2 nucleocapsid due to infection, or positive RT-PCR at scheduled visits, with absence of symptoms.

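### In Parts 1C-2 and 2, infection and asymptomatic-infection cases are limited to participants negative at baseline or pre-booster, but the rates are computed over the whole FAS

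*SAP*

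**What the plan says.** All references are to the SAP for Parts 1B, 1C, 2 and 3.

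**Who can be a case.**
- Section 3.4.3 defines asymptomatic infection in Part 2 as "counted starting 14 days after Dose 2 in participants with negative SARS-CoV-2 at baseline".
- Section 3.3.4 does the same for Part 1C-2: "counted starting 14 days after BD in participants with negative SARS-CoV-2 at baseline or prebooster".
- Section 6.5.1.2, the derivation of asymptomatic infection, counts it "in participants with negative SARS-CoV-2 status at baseline of each part".
- For overall infection, Section 6.5.1.1 states "SARS-CoV-2 infection will be defined in participants with negative SARS-CoV-2 at baseline of each part", and Table 1 has rows only for participants who start negative.
- The overall-infection entries in Sections 3.3.4 and 3.4.3 mention no status limit.

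**Who is in the denominator.**
- Section 6.5 opens with "Analyses of the exploratory efficacy endpoints (incidence rates in COVID-19, SARS-CoV-2 infection, and asymptomatic infection" and assigns the set for all three endpoints: "and using the FAS for Part 1C-2, Part 2 and Part 3".
- Section 5.1 defines that set: "The FAS for Part 2 and Part 3 consists of all participants who received at least one dose of IP in each part". For Part 1C-2 it is everyone who received the booster.
- Section 6.5.2 repeats the FAS for counts and percentages. It divides cases by total person-time from the first dose of the part.
- Section 6.1 makes the analysis set the default denominator for every percentage.

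**The concern.** The numerator and the denominator come from different populations. Someone who enters Part 2 already positive, or with status missing, cannot become an infection case under Section 6.5.1.1 or an asymptomatic case under Section 6.5.1.2. That person is still counted in the FAS and contributes follow-up until leaving the study or the cutoff. The resulting figure is neither the risk in those who could be cases nor the risk of any infection in everyone dosed.

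The SAP avoids this elsewhere. The mITT1 Sets for the long-term analysis and for Part 1C-1 (Section 5.4) exclude participants with positive or missing status. No matching set is defined for Part 1C-2 or Part 2, although positives are expected in both. The baseline-positive subset is the primary immunogenicity population in Part 2 (Section 6.4), and Part 1C-2 immunogenicity is analysed by pre-booster status (Section 5.3).

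At stake is whether these exploratory rates mean what their labels say, and whether two programmers working from the same text would produce the same table.

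**Working it through.** The SAP states no expected rate, sample size or power for these endpoints, so there is no planned figure to reproduce. The check is of the size of the dilution if Sections 6.5 and 6.5.2 are followed as written.

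**Inputs**
- Cases arise only among negatives (Sections 6.5.1.1 and 6.5.1.2).
- The denominator is the whole FAS, and person-time is total time (Sections 6.5 and 6.5.2).
- p = share of the FAS with positive or missing status. Not stated for Part 1C-2 or Part 2; assumed at 10%, 30% and 50%.
- λ = constant infection hazard among negatives. Not stated; assumed at 0.1 and 0.5 per year.
- T = follow-up of one year, equal in both groups (assumption).

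**Percentage with an event**

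FAS percentage ÷ percentage among negatives = 1 − p

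**Person-time rate**

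Per FAS participant:
- cases = (1 − p)(1 − e^(−λT))
- person-time = (1 − p)(1 − e^(−λT))/λ + pT
- ratio to the rate among negatives = cases ÷ person-time ÷ λ

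Worked example, p = 0.30 and λ = 0.1:
- 1 − e^(−0.1) = 0.0952
- cases = 0.70 × 0.0952 = 0.0666
- person-time = 0.70 × 0.952 + 0.30 = 0.966
- rate = 0.0666 ÷ 0.966 = 0.0689 per year
- ratio = 0.0689 ÷ 0.1 = 0.69

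| p | Percentage ratio | Rate ratio, λ = 0.1 | Rate ratio, λ = 0.5 |
|---|---|---|---|
| 10% | 0.90 | 0.90 | 0.88 |
| 30% | 0.70 | 0.69 | 0.65 |
| 50% | 0.50 | 0.49 | 0.44 |

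The person-time ratio falls below 1 − p because negatives stop contributing time at their event while the others run to the end of follow-up. The gap is small at a low hazard and widens as the hazard rises. If numerator, denominator and person-time are all limited to negatives, both ratios are 1.

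**The case against.** The strongest reply has four parts.

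**The derivation may not reach these parts.** Section 6.5.1.1 names only the long-term cohorts and Part 1C-1 as its populations, and its counting windows cover only those; Section 6.5.1.2 has the same windows. The COVID-19 derivations, by contrast, name Parts 1C-2, 2 and 3. Sections 3.3.4 and 3.4.3 put the negative-status limit on asymptomatic infection only. This stands in part. For asymptomatic infection the limit is explicit in both parts. For overall infection it rests on the general reference to the baseline of each part, in the only derivation the SAP provides. If that derivation does not apply, overall infection in Parts 1C-2 and 2 has none, and the text still needs correcting.

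**The endpoint wording may already restrict the denominator.** Section 6.5 leaves room for exceptions specified elsewhere, and an endpoint defined in negatives could count as one. But no restricted denominator or person-time is written for these parts, and Section 6.5.2 repeats the FAS. Subgroup analysis by baseline or pre-booster status (Section 6.1) is only optional.

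**The size is unknown.** This stands. A reader might carry over the Part 3 planning figures in Section 4.3.4 (168 of 240, or 70%, in the baseline-positive per-protocol subset) and infer a dilution of more than threefold. That is a sample-size assumption for another part, and nothing in the SAP ties it to Part 2 or Part 1C-2.

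**Nothing important depends on these rates.** Largely true. Both endpoints are exploratory, each part has one group, Part 2 is descriptive by design (Section 4.2.2), and both parts enrolled fewer than the 362 planned. Baseline or pre-booster status will also be summarised (Section 6.5), so a reader could see the positive share.

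**Conclusion.** The mismatch is real. It is firm for asymptomatic infection in Parts 1C-2 and 2. It holds for overall infection on the only derivation given, subject to reconciling that derivation with the unrestricted entries in Sections 3.3.4 and 3.4.3.

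The direction is downward whenever any FAS participant has positive or missing status. Percentages are multiplied by 1 − p, given only that cases are confined to negatives. Person-time rates are multiplied by somewhat less, on the assumptions of constant hazard and equal follow-up. The value of p cannot be taken from the documents, so 0.7 at 30% and 0.5 at 50% are illustrations.

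A reader might infer that these parts would appear better protected than they were. The SAP does not support going that far: it defines no vaccine efficacy for them and plans no comparison of their rates with those of other parts. Part 3 is outside the point, because its only listed exploratory efficacy endpoint is symptomatic COVID-19 (Section 3.5.4), which is not limited to negatives. No primary or secondary conclusion changes. The correction is still worth making, because the plan as written yields mislabelled rates.

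**What to change.** 1. In Sections 6.5 and 6.5.2, state that for SARS-CoV-2 infection and asymptomatic infection the numerator, denominator and person-time are restricted to FAS participants with negative pre-booster status (Part 1C-2) or negative baseline status (Part 2). Positive and missing status are both excluded, as in the mITT1 Sets.
2. Reconcile the overall-infection entries in Sections 3.3.4 and 3.4.3 with Section 6.5.1.1, and name Parts 1C-2 and 2 with their counting windows in Sections 6.5.1.1 and 6.5.1.2.
3. Keep the FAS for symptomatic COVID-19.

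The cost is a few sentences and one subset flag. The status definitions are already in Section 6.1 and the underlying tests are already planned. Denominators become smaller and intervals wider, in parts that are already small.

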### **6.5.1. Endpoint Definition/Derivation**

#### **6.5.1.1. Derivation of SARS-CoV-2 Infection**

This is an exploratory efficacy endpoint, which is a combination of COVID-19 and asymptomatic SARS-CoV-2 infection for participants with negative SARS-CoV-2 status at baseline (for mRNA-1273 group in long-term analysis), pre-dose 1 of mRNA-1273 (for Placebo-mRNA-1273 group in long-term analysis), or pre-booster dose (for Part 1C-1 booster dose analysis), the incidence of SARS-CoV-2 infection counted starting 14 days after the second dose of mRNA-1273 in long-term (including Part 1B), and cases counted starting 14 days after the booster dose of mRNA-1273 in Part 1C-1. SARS-CoV-2 infection will be defined in participants with negative SARS-CoV-2 at baseline of each part (pre-dose 1 of mRNA-1273 or pre-booster dose):

- bAb level against SARS-CoV-2 nucleocapsid protein negative (as measured by *Roche Elecsys*) at baseline of each part that becomes positive (as measured by *Roche Elecsys*) post-baseline, OR
- Positive RT-PCR post-baseline.

Derivation of this secondary efficacy endpoint is summarized in Table 1 below.

**Table 1. Derivation for SARS-CoV-2 Infection**

Baseline SARS-CoV-2 Status	Post-baseline assessments		Endpoint: SARS-CoV-2 infection
	PCR test post baseline	bAb levels against SARS-CoV-2 Nucleocapsid	
Negative at Baseline of each part	Positive (either at scheduled NP swab test, or at exposure or symptom-prompt NP swab test)		Case

Negative at Baseline of each part	Positive (at scheduled post-baseline visits) as measured by Roche Elecsys	Case
--------------------------------------	---	------

The date of documented infection will be the earlier of:

- Date of positive post-baseline RT-PCR result, or
- Date of positive serology test result based on bAb specific to SARS-CoV-2 nucleocapsid

In long-term analysis (including Part 1B), SARS-CoV-2 infection cases will be counted starting 14 days after the second injection of mRNA-1273, i.e. date of documented infection - Date of the 2nd injection  $\geq$  14. SARS-CoV-2 infection cases will also be summarized based on tests performed at least 14 days after first dose of IP.

In Part 1C-1, SARS-CoV-2 infection cases will be counted starting 14 days after the booster dose of mRNA-1273, i.e. date of documented infection - Date of the booster injection  $\geq$  14.

#### **6.5.1.2. Derivation of Asymptomatic SARS-CoV-2 Infection**

This is an exploratory efficacy endpoint: the incidence of asymptomatic SARS-CoV-2 infection measured by RT-PCR and/or serology tests obtained at post-baseline visits counted starting 14 days after the second injection of mRNA-1273 in long-term (including Part 1B), and cases counted starting 14 days after the booster dose of mRNA-1273 in Part 1C-1, in participants with negative SARS-CoV-2 status at baseline of each part.

Asymptomatic SARS-CoV-2 infection is identified by absence of symptoms and infections as detected by RT-PCR or serology tests. Specifically:

- Absent of COVID-19 symptoms
- AND at least one from below:
  - bAb level against SARS-CoV-2 nucleocapsid protein negative (as measured by Roche Elecsys) at baseline of each part that becomes positive (as measured by Roche Elecsys) post-baseline, OR
  - Positive RT-PCR test post-baseline (at scheduled or unscheduled/illness visits)

The date of documented asymptomatic infection is the earlier date of positive serology test result based on bAb specific to SARS-CoV-2 nucleocapsid due to infection, or positive RT-PCR at scheduled visits, with absence of symptoms.

#### 6.5.1.3.Derivation of COVID-19

This is a exploratory efficacy endpoint: the incidence of the first occurrence of COVID-19 starting 14 days after the second dose of IP in long-term (including Part 1B), Part 2 and Part 3, cases counted starting 14 days after the first dose of IP in Part 3, and cases counted starting 14 days after the booster dose of mRNA-1273 in Part 1C-1 and Part 1C-2.

COVID-19 is defined as symptomatic disease based on the criteria specified in [Section 3.2](#). Cases are defined as participants meeting clinical criteria based on both symptoms for COVID-19 and positive RT-PCR test results.

Surveillance for COVID-19 symptoms will be conducted via biweekly telephone calls or eDiary. Subjects reporting COVID-19 symptoms, as defined in [Section 7.3.2 of the protocol](#), will be arranged an illness visit to collect an NP swab.

For this efficacy endpoint, a COVID-19 case will be identified as a positive post-baseline RT-PCR test result, together with eligible symptoms, i.e. a positive PCR result of the eligible symptoms summarized below in Table 2.

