#### **4.1.1.1. Part 1A, the Blinded Phase**

The Blinded Phase of this study is a randomized, observer-blind, placebo-controlled study intended to infer the effectiveness of mRNA-1273 in an adolescent population aged 12 to < 18 years. The study includes 2 arms: (i) 100 µg of mRNA-1273, and (ii) placebo.

[figure not shown]
Approximately, 3000 participants 12 to < 18 years of age will be randomly assigned in a 2:1 ratio to receive mRNA-1273 (n=2000) or placebo (n=1000).

The schematic of study arms and major study events for Part 1A is illustrated in [Figure 2](#) and the Schedule of Assessments is provided in [Appendix E](#).

The goal of the study is to seek an indication for use of mRNA-1273 (100 µg IM, given as 2 injections, 28 days apart) in the 12 to < 18 years age group. Each participant will receive one injection of mRNA-1273 or placebo on Day 1 and Day 29 and then be followed up for a total of 12 months following the second injection.

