### **5.2. Full Analysis Set**

The Full Analysis Set (FAS) consists of all randomized participants who received at least one dose of IP. Participants will be analyzed according to the treatment group to which they were randomized.

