## **6.6. Long-term Analysis (including Part 1B)**

Long-term analysis will be performed including data collected in the Open-label Observational Phase (Part 1B), and prior to BD if a BD is received. The analysis will include participants who received mRNA-1273 in Part 1A and remained in the study with or without unblinding, and participants who received placebo in Part 1A and received mRNA-1273 in Part 1B after unblinding. Long-term analysis of applicable safety, efficacy, and immunogenicity endpoints will be summarized descriptively by treatment cohort without treatment group comparison.

In the long-term safety analysis, unsolicited AEs (SAE, AESI, MAAE, and AE leading to discontinuation) and deaths will be summarized.

In the long-term immunogenicity analysis, nAb and bAb values will be summarized at specified timepoints.

In the long-term efficacy analysis, the incidence rates of COVID-19 and of SARS-CoV-2 infection cases will be counted starting 14 days after the second dose of IP for participants in treatment cohorts of mRNA-1273 and Placebo, or starting 14 days after the second dose of mRNA-1273 for participants in the Placebo-mRNA-1273 Cohort. Incidence rate with 95% CI adjusting for person-time will be provided. The incidence rate of asymptomatic SARS-CoV-2 infection will also be provided.

Incidence rate will be analyzed by calendar month in the Long-term analysis.

Additional details for the Long-term analysis will be provided in a separate SAP (Part 1B, Part 1C, Part 2 and Part 3).

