2. All scheduled study visits should be completed within the respective visit windows. If the participant is not able to attend a study site visit as a result of the COVID-19 pandemic (self-quarantine or disruption of study site activities following business continuity plans and/or local government mandates for “stay at home” or “shelter in place”), a safety telephone call to the participant should be made in place of the study site visit. The safety telephone call should encompass all scheduled visit assessments that can be completed remotely, such as assessment for AEs and concomitant medications (e.g., as defined in scheduled safety telephone calls). Home visits will be permitted for all nondosing visits, except for Screening, if a participant cannot visit the study site due to the COVID-19 pandemic. Home visits must be permitted by the study site IRB and the participant via informed consent/assent and have prior approval from the Sponsor (or its designee).
3. If the visit for the second dose (Day 29) is disrupted and cannot be completed at Day 29 +7 days due to the COVID-19 pandemic (self-quarantine or disruption of study site activities following business continuity plans and/or local government mandates for “stay at home” or “shelter in place”), the visit window may be

extended to Day 29 + 21 days. When the extended visit window is used, the remaining study visits should be rescheduled to follow the inter-visit interval from the actual date of the second dose.

4. Safety follow-up via an eDiary questionnaire will be performed every 4 weeks from Day 71 to Day 183 and again from Day 223 to Day 363.
5. Safety follow-up via a safety telephone call will be performed every 4 weeks from Day 85 to Day 197 and again from Day 237 to Day 377.
6. The Participant Decision Visit may be performed over multiple visits. Once the Participant Decision Visit has been initiated, all assessments must be completed within a 7-day period.

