### **3. Study Endpoints**

#### **3.1. Part 1B, Open Label**

##### **3.1.1. Exploratory Endpoints**

The exploratory endpoints are the following:

- MAAEs through the last day of study participation or the booster dose if applicable
- SAEs through the last day of study participation or the booster dose if applicable
- AESIs through the last day of study participation or the booster dose if applicable
- AEs leading to discontinuation from study participation through the last day of study participation or the booster dose if applicable
- The incidence of SARS-CoV-2 infection (symptomatic or asymptomatic infection) counted starting 14 days after the second dose and after the first dose of mRNA-1273, including Part 1A and Part 1B for mRNA-1273 cohort, and Part 1B for placebo-mRNA-1273 cross-over cohort
- To evaluate the incidence of asymptomatic SARS-CoV-2 infection after vaccination with mRNA-1273 measured by RT-PCR and/or bAb levels against SARS-CoV-2 nucleocapsid protein (by Roche Elecsys) counted starting 14 days after the second dose and after the first dose of mRNA-1273 in participants with

negative SARS-CoV-2 at baseline, including Part 1A and Part 1B for mRNA-1273 cohort, and Part 1B for placebo-mRNA-1273 cross-over cohort

- The incidence of the first occurrence of symptomatic COVID-19 starting 14 days after the second dose and after the first dose of mRNA-1273, including Part 1A and Part 1B for mRNA-1273 cohort, and Part 1B for placebo-mRNA-1273 cross-over cohort

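### Section 6.5.1.3 of the later-parts SAP anchors the long-term COVID-19 count on the second dose of IP, contradicting the second-dose-of-mRNA-1273 anchor set elsewhere for the crossover cohort

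*SAP*

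**What the plan says.** The document holds two plans, one for Part 1A and one for Parts 1B, 1C, 2 and 3 (the later-parts SAP). They give the start of the long-term COVID-19 count in three places:

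- Later-parts SAP, Section 6.5.1.3 (derivation): "starting 14 days after the second dose of IP in long-term (including Part 1B), Part 2 and Part 3".
- Later-parts SAP, Section 3.1.1 (endpoint): "starting 14 days after the second dose and after the first dose of mRNA-1273", with only Part 1B counted for the crossover cohort.
- Part 1A SAP, Section 6.6: the second dose of IP for the mRNA-1273 and Placebo cohorts, "or starting 14 days after the second dose of mRNA-1273 for participants in the Placebo-mRNA-1273 Cohort".

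In the later-parts SAP, the derivations of SARS-CoV-2 infection (6.5.1.1, main rule) and asymptomatic infection (6.5.1.2) also use the second injection of mRNA-1273. Section 6.5.1.1 then adds a supplementary count that returns to IP: "SARS-CoV-2 infection cases will also be summarized based on tests performed at least 14 days after first dose of IP".

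IP covers placebo in this study. The Part 1A Full Analysis Set is "all randomized participants who received at least one dose of IP", and Section 4.1.1.1 of the Part 1A SAP says: "Each participant will receive one injection of mRNA-1273 or placebo on Day 1 and Day 29".

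**The concern.** A crossover participant had two placebo injections in Part 1A before receiving any mRNA-1273. Counting doses of IP from study entry, the second one is placebo, and the 14-day condition has expired months before crossover. It would then exclude nothing for this cohort. For the mRNA-1273 cohort the second dose of IP is the second dose of vaccine, so the condition works as intended and the count starts at about Day 43.

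At stake is the incidence rate reported for the Placebo-mRNA-1273 cohort. It would include cases from the weeks before 14 days after the second vaccine dose, while the rate for the mRNA-1273 cohort would not. Two programmers working from different sections could produce different counts and each point to the plan.

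**Working it through.** The plan gives no figure to reproduce here. The check is date arithmetic and a comparison of sections.

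**Inputs**
- Second Part 1A dose: Day 29, with +7 days allowed (Day 36). Under pandemic disruption this may be "extended to Day 29 + 21 days", that is Day 50 (Part 1A SAP, Appendix E).
- First crossover dose (OL-D1): about D209, window −56/+56, so D153 to D265 (Appendix F).
- Second crossover dose: OL-D29, window −3/+7, so OL-D26 to OL-D36 (Appendix F).
- Long-term efficacy period: opens at the first dose of mRNA-1273 (later-parts SAP, Section 6.1, analysis periods).
- Person-time: starts at the first dose of each part (later-parts SAP, Section 6.5.2).

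**Step 1. Is the literal condition already met at crossover?** Gap = OL-D1 minus the day of the second placebo dose.
- Nominal: 209 − 29 = 180 days.
- Shortest: 153 − 50 = 103 days.
- Longest: 265 − 29 = 236 days.

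Every value exceeds 14, so the literal condition is always met by OL-D1. Because the analysis period opens at the first mRNA-1273 dose, cases would count from OL-D1.

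**Step 2. Where does the count start on the mRNA-1273 anchor?** Start = day of the second crossover dose + 14.
- Nominal: OL-D29 + 14 = OL-D43, so 42 days (OL-D1 to OL-D42) are admitted only by the literal reading.
- Early dose: OL-D26 + 14 = OL-D40, 39 extra days.
- Late dose: OL-D36 + 14 = OL-D50, 49 extra days.

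**Step 3. What happens to the rate?** Person-time starts at the same date on both readings, so the change is essentially all in the numerator. Assume constant exposure over OL-D1 to OL-D178 (177 days; 177 − 42 = 135 days after the intended start), with protection e1 before and e2 after that start:

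ratio of cases = [42(1 − e1) + 135(1 − e2)] / [135(1 − e2)]

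| e1 | e2 | Calculation | Ratio |
|---|---|---|---|
| equal to e2 | any | 177/135 | 1.31 |
| 0.5 | 0.9 | (21 + 13.5)/13.5 | 2.56 |
| 0.3 | 0.9 | (29.4 + 13.5)/13.5 | 3.18 |
| 0.5 | 0.7 | (21 + 40.5)/40.5 | 1.52 |
| 0.3 | 0.5 | (29.4 + 67.5)/67.5 | 1.44 |

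The documents give no value for e1 or e2; all are assumptions.

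**Step 4. The supplementary count in Section 6.5.1.1.** On the same literal reading, the first dose of IP is the Day 1 placebo. Cases would count from OL-D1 instead of OL-D15, which adds about 14 days.

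**The case against.** The strongest reply is that the plan already fixes the anchor. Section 3.1.1 of the same SAP defines the endpoint by doses of mRNA-1273. Section 6.6 of the Part 1A SAP states the rule for the Placebo-mRNA-1273 cohort by name. Section 6.5.1.3 can also be read by study part: the parallel CDC-case derivation in 6.5.1.4 ties the second dose of IP to Part 1B, where every dose is mRNA-1273, and IP is a natural umbrella term in a sentence that also covers mRNA-1273.222 in Part 3. The Full Analysis Set wording used above to show that IP includes placebo comes from the Part 1A SAP.

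Much of this stands. A reader might infer that the plan as a whole counts crossover cases from the first vaccine dose. It does not; the fault is a contradiction whose intended resolution is visible.

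The reply does not make 6.5.1.3 sound. Section 6.1 of the later-parts SAP defines the long-term analysis as Part 1A plus Part 1B, so the phrase used in 6.5.1.3 does not confine the dose to Part 1B as 6.5.1.4 does. Section 6.6 of the Part 1A SAP itself separates doses of IP from doses of mRNA-1273 for exactly this cohort, and it leaves further detail to the later-parts SAP. That SAP gives no precedence between its endpoint and derivation sections, and 6.5.1.3 has no date formula of the kind that settles the main rule in 6.5.1.1.

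**Conclusion.** The contradiction is real and should be removed; its consequence is conditional. If 6.5.1.3 is programmed literally, 42 extra days of crossover cases (39 to 49) enter the numerator and the cohort's incidence rate is too high. The increase is about 1.3-fold if exposure is constant and protection is the same before and after 14 days post dose 2, and larger if early protection is lower. A reader might take the 2.6-fold result as the expected error, but it requires assumed protection of 50% early and 90% late, and other plausible pairs give about 1.4 to 1.5.

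A reader might also infer a biased comparison between the two cohorts. The plan makes no such formal comparison: the endpoint is exploratory, Section 6.6 of the Part 1A SAP calls for descriptive summaries without treatment group comparison, and Section 6.5.2 of the later-parts SAP plans only incidence rates with confidence intervals. No hypothesis, alpha or power is touched.

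**What to change.** In Section 6.5.1.3 of the later-parts SAP, for the long-term analysis (including Part 1B), replace *second dose of IP* with *second dose of mRNA-1273*, keeping IP for Part 2 and Part 3. In the supplementary count of Section 6.5.1.1, replace *first dose of IP* with *first dose of mRNA-1273*. Both then agree with Section 3.1.1, and the second-dose rule also agrees with Section 6.6 of the Part 1A SAP. The cost is two wording changes and a check that the analysis programs use the mRNA-1273 dose dates for the crossover cohort.
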